***Do not dose patient on Baseline visit if the patient opted for LP. Refer to Visit 2.5 instead**

- Inclusion/exclusion check
- Concomitant medication reconciliation
- Labs (CBC w/ diff, CMP, TSH)
- Labs (PT, PTT, INR) to be completed and reviewed pre-lumbar puncture for all lumbar punctures
- Optical Coherence Tomography (OCT) Eye Exam (must be done before dose)
- Serum pregnancy test (if applicable)
- EKG (EKG to be completed at pre- and 6-hours post-dose \pm 10 minutes)
- Vital signs including weight
- Vital signs, post-dose, every hour for 6 hours \pm 10 minutes
- Neuro and physical exam
- Cognitive assessments for data collection only (MMSE, ADAS-cog 13, CDR, ADCS-ADL)
- Volumetric MRI (+ 4 weeks window) if vMRI was not completed during Screening
- Blood biomarkers
- Randomization*
- Dispense study drug, patient dose to be completed in-clinic*
- Drug diary provided to patient*
- Drug accountability including instructions on how to take treatment drug*
- Adverse event Assessment

The following are to be completed if participants opted into one, or both, of the optional studies:

- Lumbar puncture followed by phone check in 24hrs-48 hrs post-lumbar puncture
- Saliva collection pre- treatment dose

Visit 2.5 at Day 1 of dosing, Baseline Visit, 0.25mg/day (Only for patients who undergo LP at Baseline)

- Vital signs including weight (pre-dose), hourly vital signs \pm 10 minutes (post-dose observation for 6 hours)
- EKG (pre-dose and post-dose at 6 hours \pm 10 minutes)
- Randomization
- Dispense study drug, patient dose to be completed in-clinic
- Drug diary provided to patient
- Drug accountability including instructions on how to take treatment drug
- Adverse event assessment

Every effort will be made to complete baseline visits in the morning to allow for ample time to monitor participants after the first visit. Subjects will be administered first treatment dose in clinic and will be monitored for the following 6 hours. Every hour subjects will undergo BP/HR monitoring and AE symptom check. Investigator will be notified of BP/HR each hour with HRs rate less than 55 BPM being indicative of immediate intervention by investigator.

At the 6-hour mark after first dose participant will undergo an EKG for safety monitoring. Investigators will review EKG results for bradyarrhythmia and prolonged QT interval. Review of EKG will be completed prior to participant leaving clinic for participant safety.

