Prior to leaving, patients will be given a sufficient supply of study medication (or placebo) to last until the next in-clinic visit at Visit 3 along with instructions for their use. Patients should be instructed to take their medication every morning thereafter at or around the same time.

If a titration dose is missed, or if 4 or more consecutive daily doses are missed during treatment, restart at last dose taken.

Telephone visits at Day 7,21,35,49,63,84,140,196,252, and 308 (± 7 days)

Telephone visits will be used between dose increases to monitor any safety events with participants. In addition, telephone visits will serve as safety check-in.

The following procedures will be performed at all scheduled telephone visits as shown in the schedule of events:

- Medication reconciliation
- AE assessment

Visit 3 at Day 14 (± 7 days) 0.50mg/day

The following tests and procedures will be completed in clinic:

- Concomitant medication reconciliation
- Labs (CBC w/ diff, CMP, TSH)
- EKG (pre-dose, post-dose at 6-hours ± 10 minutes)
- Vital signs including weight (pre-dose)
- Vital signs (post-dose every hour ± 10 minutes for 6 hours)
- Neuro and physical exam
- Blood biomarkers
- Dispense study drug and drug diary
- Drug accountability
- Adverse event assessment

Visit 4 at Day 28 (± 7 days) 0.75mg/day

The following tests and procedures will be completed in clinic:

- Concomitant medication reconciliation
- Labs (CBC w/ diff, CMP, TSH)
- EKG (pre-dose, post-dose at 6-hours ± 10 minutes)
- Vital signs including weight (pre-dose)
- Vital signs (post-dose every hour ± 10 minutes for 6 hours)
- Neuro and physical exam
- Blood biomarkers
- Dispense study drug and drug diary in clinic
- Drug accountability
- Adverse event assessment

Visit 5 at Day 42 (± 7 days) 1 mg/day

The following tests and procedures will be completed in clinic:

- Concomitant medication reconciliation
- Labs (CBC w/ diff, CMP, TSH)
- EKG (pre-dose, post-dose at 6-hours ± 10 minutes)
- Vital signs including weight (pre-dose)

- Vital signs (post-dose every hour \pm 10 minutes for 6 hours)
- Neuro and physical exam
- Blood biomarkers
- Dispense study drug and drug diary in clinic
- Drug accountability
- Adverse event assessment

Visit 6 at Day 56 (\pm 7 days) 1 mg/day

The following tests and procedures will be completed in clinic:

- Concomitant medication reconciliation
- Labs (CBC w/ diff, CMP, TSH)
- EKG
- Vital signs including weight
- Neuro and physical exam

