1.2 SCHEDULE OF EVENTS (SOE)

The Schedule of Events is summarized in tabular form above and detailed below in table 1. All subjects will be expected to complete all evaluations in study.

Table 1: Study Schedule of Events

Study Visit	Screening Visit	0.25 mg/day		0.50 mg/day		0.75 mg/day		1 mg/day						
		Baseline Visit	Phone Visit	Visit 3	Phone Visit	Visit 4	Phone Visit	Visit 5	Phone Visit	Visit 6	Phone Visit	Visit 7	Phone Visit	Visit 8
Study Day (+/- 7 days)	-56 to 0	1	7	14	21	28	35	42	49	56	63	70	84	112
Study Week		0	1	2	3	4	5	6	7	8	9	10	12	16
Informed Consent	X													
Eligibility Criteria	X													
CYP2C9 genotyping	X													
Medical History	X	X	X	X	X	X	X	X	X	X	X	X	X	X
Concomitant Medications	X	X	X	X	X	X	X	X	X	X	X	X	X	X
Labs (CBC, CMP, TSH)	X	X		X		X		X		X		X		X
Coagulation panel (PT, PTT, INR)	X ^e	X ^e												
Serum Pregnancy Test	X ⁱ	X ⁱ												
EKG	X	X ^h		X ^h		X ^h		X ^h		X		X		X
Vital signs, Height/Weight	X ^k	X ^{mk}		X ^{mk}		X ^{mk}		X ^{mk}		X ^k		X ^k		X ^k
Neuro and Physical Exam	X	X		X		X		X		X		X		X
Cognitive Assessments	X ^a	X ^{b,c}												
Eye exam (OCT)		X ⁿ								X				
MRI (preferred) or CT scan ^g	X ^g													
Randomization		X												
Volumetric MRI		X ^o												
Blood biomarkers		X		X		X		X		X		X		X
(Optional) Saliva		X ^r												
(Optional) Lumbar Puncture ^d		X ^{d,e,r,s}												
Drug Accountability		X		X		X		X		X		X		X
Adverse Event Assessment		X	X	X	X	X	X	X	X	X	X	X	X	X
Dispense Study Drug and Drug Diary		X ^s		X		X		X		X		X	X	X

a. Screening MMSE, Hachinski, Geriatric Depression Scale (GDS), and CSSR-S

b. ADCOMS (MMSE, ADAS-Cog 13, CDR-SOB)

c. ADCS-ADL

d. All lumbar punctures will be followed by phone call 24-48hrs after lumbar puncture to ensure participant safety

e. Drawn only if opted in for LP. Results required before LP is completed schedule

f. Dispense of visit drug and first treatment to be completed in clinic

g. If not done within 12 months. Study willing to accept historical CT if done in past 12 months

h. EKG 6 hour post-dose observation. ±10 minutes

i. If participant is of child-bearing potential

k. Height will only be recorded at screening

m. Post-dose vitals every hour ±10 minutes

n. Eye exam (OCT) must be pre-dose

o. vMRI can be done within window of 4 weeks

p. End of study vMRI can be done within window of ±4 weeks

r. Optional substudy procedure if patient opts in

s. If patients opt in for LP on Baseline visit

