3. RISK/BENEFIT ASSESSMENT

3.1.1 KNOWN POTENTIAL RISKS

Siponimod (formerly known as BAF312 and completed trial NCT #01665144) has been FDA approved since 2019 (IND #076122) for the treatment of multiple sclerosis. Most adverse events have been reported from MS patients, and very little is known about possible adverse events in subjects without MS. Most risks are associated with doses >2 mg/day. Most common adverse reactions (reported in >5%) are headache, hypertension, and transaminase increase (see Table 2).

Table 2: Summary of Adverse Events Reported in $\geq 5\%$ of Mayzent treated patients at a rate of at least 1% higher than in patients receiving placebo

Adverse reaction	MAYZENT 2 mg (N=1099) %	Placebo (N=546) %
Headache ^a	15	14
Hypertension ^b	13	9
Transaminase increased ^c	11	3
Falls	11	10
Peripheral edema ^d	8	4
Nausea	7	4
Dizziness	7	5
Diarrhea	6	4
Bradycardia ^e	6	3
Pain in extremity ^f	6	4

Terms were combined as follows:

- Headache, tension headache, sinus headache, cervicogenic headache, drug withdrawal headache, and procedural headache.
- Hypertension, blood pressure increased, blood pressure systolic increased, essential hypertension, blood pressure diastolic increased.
- Alanine aminotransferase increased, gamma-glutamyl transferase, increased hepatic enzyme increased, aspartate aminotransferase increase, blood alkaline phosphatase increase, liver function test increased, hepatic function abnormal, liver function test abnormal, transaminases increased.
- Peripheral edema, joint swelling, fluid retention, swelling face
- Bradycardia, sinus bradycardia, heart rate decreased
- Pain in extremity and limb discomfort

POTENTIAL SERIOUS ADVERSE EVENTS

+ *Bradycardia, Bradyarrhythmia, and Atrioventricular Conduction Delays*

Siponimod may cause the heart rate to slow, especially after taking the first dose. This issue will be mitigated by administering an EKG post dose at the 6-hour mark to assess for any potential adverse events. In addition, BP/HR will be checked hourly for 6 hours to assess for potential bradyarrhythmia or adverse events.

+ *Infections*

Siponimod lowers the number of lymphocytes, which may increase the risk of serious infections. Lymphocyte levels will be monitored by measuring a Complete Blood Count with differential at each in-clinic study visit.

+ *Liver Injury*

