Summary statistics for actual values and for changes from baseline will be tabulated for laboratory results by scheduled visit. Subjects with clinical laboratory values outside of the normal reference range at any post-baseline assessment will be summarized. Shifts from baseline laboratory values (to worst severity per subject) will be tabulated.

- Electrocardiogram Results

The EKG parameters (heart rate, PR interval, QRS interval, QT interval, and QTc interval) at each time recorded (scheduled for screening and study end) as well as the change from screening will be summarized with descriptive statistics.

The overall EKG assessment will be reported as “Normal” or “Abnormal” with respect to relevant abnormalities by the investigator. A shift table comparing the EKG assessment over the treatment period (every abnormal) to screening will be presented.

- Vital Signs

The observed data at baseline and change from baseline for each measurement day will be summarized with descriptive statistics.

BASELINE DESCRIPTIVE STATISTICS

The distributions of patients completing each study visit and the reason for early terminations will be tabulated for each treatment group. The duration of double-blind treatment within each treatment group and compliance rates will be summarized by descriptive statistics (mean, standard error, standard deviation, median, minimum, maximum, and sample size) for days of treatment, for total days of exposure, and by the distributions of patients exposed to various durations of treatment categories. Demographic and baseline characteristics will be summarized by descriptive statistics for all patients in each treatment group.

PLANNED INTERIM ANALYSES

Formal interim analyses are not planned. Data will be reviewed by the DSMB for their assessment of safety and risk/benefit considerations.

SUB-GROUP ANALYSES

No sub-group analyses are planned.

TABULATION OF INDIVIDUAL PARTICIPANT DATA

Participant data will be listed by measure and time point.

EXPLORATORY ANALYSES

Statistical analysis of the exploratory CSF, blood, and saliva biomarkers will be carried out by our biostatistician. Comparisons will assess the change from baseline for the following markers assessed at the frequency indicated in the schedule of visits Table 1):

- Alzheimer's Disease Cooperative Study- Activities of Daily Living (ADCS-ADL)
- blood inflammatory markers (e.g., TNF- α , IL-1 β , IL-6)
- CSF and plasma C-reactive protein
- CSF and plasma TNF- α

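### The by-day vital-signs summary does not match the hourly post-dose readings on the four dose-step days and leaves the first-dose heart-rate response without a defined summary

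*Protocol*

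**What the plan says.** Section 12, Safety Analyses, Vital Signs, is a single sentence: "The observed data at baseline and change from baseline for each measurement day will be summarized with descriptive statistics". It does not define baseline, mention time points within a day, or say how repeated readings on one day are handled.

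The collection plan is finer. In Section 1.1, the Baseline visit has "Vital signs, post-dose, every hour for 6 hours". Visit 2.5, used when a participant has a baseline lumbar puncture, has the same hourly observation. Visits 3, 4 and 5 each have a pre-dose set and then "Vital signs (post-dose every hour" for six hours. Footnote m of the schedule in Section 1.2 ("Post-dose vitals every hour") marks the same four occasions. On the first-dose day, "Every hour subjects will undergo BP/HR monitoring and AE symptom check", with "HRs rate less than 55 BPM being indicative of immediate intervention by investigator".

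Section 3.1.1 gives the reason: "Siponimod may cause the heart rate to slow, especially after taking the first dose", and so "BP/HR will be checked hourly for 6 hours to assess for potential bradyarrhythmia or adverse events". The synopsis names vital signs and EKGs among the components of the primary safety endpoint.

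**The concern.** The hourly readings exist to detect an acute response within hours of a dose. The stated analysis works in days and refers everything to one study baseline. If the sentence is followed literally, the measurement designed to show first-dose heart-rate slowing has no defined summary.

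The matter is central to this trial. Safety is the primary objective. The dose justification in Section 6 says there is no literature on possible cardiac adverse events of siponimod in adults over 60 and uses this to support a low dose. A comparison of the acute heart-rate response between arms is therefore among the more useful safety results the trial could give. Its form should be settled before unblinding.

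**Working it through.** No figure in the protocol is in dispute. The check sets the collection beside the analysis.

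**Readings collected** (Sections 1.1 and 1.2)
- Dose-step days: Baseline or Visit 2.5, Visit 3, Visit 4, Visit 5 = 4.
- Post-dose sets per day: 6. Per participant: 4 × 6 = 24, or 24 + 4 = 28 with the pre-dose sets.
- For 105 participants with full attendance: 105 × 24 = 2,520 post-dose sets.

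**Unit of analysis** (Section 12)
- Laboratory values are summarised by scheduled visit, EKG parameters at each recorded time, and listings by measure and time point. Vital signs alone are summarised by measurement day, although they are the measure taken most often within a day.

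**Day 1**
- For participants without a lumbar puncture, Day 1 is both the baseline day and the first-dose day. At least three summaries fit the sentence:
  1. Each hourly reading is tabulated against the pre-dose value. The first-dose response is shown in full.
  2. One averaged value is given for the day. A fall of D bpm lasting h of the 6 hours appears as D × h/6. For an assumed 10 bpm fall this gives 1.7 (h = 1), 3.3 (h = 2), 5.0 (h = 3) or 10 (h = 6).
  3. Only the pre-dose value is used. The Day 1 change is zero by construction.
- The protocol does not choose among these. The averaging rule and the 10 bpm fall are assumptions used to show the range; neither is in the protocol.
- Participants having a baseline lumbar puncture have vital signs at the Baseline visit and again before dosing at Visit 2.5, 24 to 48 hours after the puncture. They have two candidate baselines, and Section 12 does not say which applies.

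**Visits 3 to 5** (Days 14, 28 and 42)
- Change from study baseline at hour t = (same-day pre-dose − study baseline) + (reading at hour t − same-day pre-dose).
- The second term is the acute effect of the new step. The first is the change accumulated over the preceding 2, 4 or 6 weeks. The stated summary reports only the sum, although the same-day pre-dose value needed to separate the terms is collected.

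**Other routes to the signal**
- Adverse-event tables: these count what is recorded as an adverse event. Section 2.2 reports that, in the trial of the related drug in amyotrophic lateral sclerosis, three participants had transient bradycardia in the hours after the first dose without clinical symptoms. Section 1.1 does not make a heart rate below 55 BPM an adverse event in itself.
- EKG heart rate: Section 12 refers change to screening, which may be up to 56 days before dosing. It describes EKGs as scheduled at screening and study end, whereas Sections 1.1 and 1.2 schedule pre-dose and 6-hour post-dose EKGs at all four steps and EKGs at the later clinic visits.
- Listings: these keep every hourly value but do not compare arms.

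**The case against.** The strongest objection is that the defect is partly read into the text. A reader might infer that each day is reduced to one value, so that the heart-rate signal is averaged away or left out. The protocol does not support this: it states no averaging, no single daily value and no exclusion of post-dose readings. Tabulating every hour within each day also satisfies the sentence, and nothing would then be lost. A reader might likewise infer that the trial could not show whether heart rate fell. That is too strong. Adverse events are tabulated by treatment received, and the definition of an adverse event includes abnormal findings. EKG heart rate is summarised, the safety board reviews safety data, and individual values are listed by time point. This part of the objection stands.

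It can also be said that nadirs, hourly tables and threshold counts belong in a statistical analysis plan, which is not shown here. That is fair as to detail. But the protocol does more than stay silent: it names a unit and a reference that do not fit the data it collects, and a later plan would have to interpret or depart from them.

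Finally, study baseline is a conventional reference, and the placebo arm provides a comparator for drift. This stands for drift common to both arms. It does not separate the acute effect of a new step from a lasting effect of earlier steps, which occurs only on active drug. The 55 BPM level is a real-time prompt stated for the first-dose day, not an analysis criterion, so any use of it in a table should be descriptive only.

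**Conclusion.** The point holds as a mismatch between analysis wording and data collection. The stated by-day change from baseline gives the Day 1 first-dose response no defined summary, leaves baseline ambiguous for participants having a lumbar puncture, and at Visits 3 to 5 does not isolate the acute effect of each dose step. The other safety outputs reduce the gap without closing it: they can miss symptom-free falls, do not compare arms hour by hour, or use a distant reference.

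The size of any loss cannot be stated, because it depends on a handling rule the protocol does not give. It ranges from none, if hourly values are tabulated, to the whole Day 1 response, if only pre-dose values are used. This is an inexpensive improvement to the analysis of a primary-endpoint measure. It is not evidence that the safety assessment fails.

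**What to change.** In Section 12, Vital Signs:
- Define baseline as the pre-dose reading on the first-dosing day (Visit 2.5 for participants having a baseline lumbar puncture).
- For the four dose-step days, summarise by arm and hour the change from the same-day pre-dose value. Add each participant's maximum post-dose fall in heart rate and maximum change in blood pressure.
- Give the number and percent in each arm with any post-dose heart rate below the 55 BPM level already in Section 1.1, as a descriptive count only. This carries no implication for clinical management.
- Keep the by-day summary for all other visits.

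In Section 12, Electrocardiogram Results, reconcile the description of when EKGs are scheduled with the pre-dose and 6-hour post-dose EKGs in Sections 1.1 and 1.2.

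The cost is a few sentences and a few extra tables. No dose, visit or procedure changes, and the data are already collected.

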14. ABBREVIATIONS

Abbreviation	Term
A β	Amyloid Beta
AD	Alzheimer's Disease
ADAS	Alzheimer's Disease Assessment Scale
ADAS-Cog	Alzheimer's Disease Assessment Scale – Cognitive subscale
ADCS-ADL	Alzheimer's Disease Cooperative Study - Activities of Daily Living
AE	Adverse Event
ALS	Amyotrophic lateral sclerosis
ALT	Alanine aminotransferase
aMCI	Amnesic mild cognitive impairment
ANDA	Abbreviated New Drug Application
Anti HCV	Hepatitis C Antibody
ApoE	Apolipoprotein subtype E
APP	Amyloid precursor protein
ARIA-E	Amyloid-related imaging abnormalities - edema/effusions
ARIA-H	Amyloid-related imaging abnormalities - hemosiderin deposition
BACE1	Beta amyloid precursor protein cleaving enzyme 1
BP	Blood pressure
CBC w/ diff	Complete blood count with differential
CDSCO	Central Drugs Standard Control Organization
CDR	Clinical Dementia Rating Scale
CDR-SOB	Clinical Dementia Rating Scale - Sum of Boxes
C _{max}	Maximum plasma concentration
CMH	Cerebral microhemorrhage
CMP	Comprehensive metabolic panel
CNS	Central nervous system
CONSORT	Consolidated Standards of Reporting Trials
CRF	Case report form
CRO	Contract Research Organization
CRP	C reactive protein
CSE	Clinically significant event
CSF	Cerebrospinal fluid
CT	Computed Tomography
CVA	Cardiovascular Accident
CVE	Cerebral Vasogenic Edema
DOB	Date of Birth
DSMB	Data Safety Monitoring Board
DSM	Diagnostic and Statistical Manual of Mental Disorders
eCRF	Electronic Case Report Form
EDTA	Ethylenediaminetetraacetic Acid
EKG	Electrocardiogram
ELISA	Enzyme-linked immunosorbent assay
EMA	European Medicines Agency
FBRP-PET	Florbetapir- Positron Emission Tomography
FDA	Food and Drug Administration
Abbreviation	Term

FLAIR	Fluid-Attenuated Inversion Recovery image
FSH	Follicular Stimulating Hormone
FTD	Frontotemporal dementia
FOV	Field of View
GCA	Global Cortical Average
GCP	Good Clinical Practice
G-CSF	Granulocyte-colony stimulating factor
GDS	Geriatric Depression Scale
GWAS	Genomic-Wide Association Studies
HC	Hippocampus
Hep	Hepatitis
HIPAA	Health Insurance Portability and Accountability Act
HIV	Human Immunodeficiency Virus
ICH	International Conference on Harmonization
IEC	Independent Ethics Committee
IFN	Interferon
IND	Investigational New Drug
IL	Interleukin
IRB	Institutional Review Board
IV	Intravenous
LAR	Legally authorized representative
LP	Lumbar puncture
MCI	Mild cognitive impairment
MDS	Myelodysplastic Syndrome
MedDRA	Medical Dictionary for Regulatory Activities
MOP	Manual of Operations
MM	Multiple myeloma
